## **9.7 Sedative & anaesthetic agents for bronchoscopy**

Fentanyl is a licensed opioid used routinely to provide analgesia and sedation during medical procedures. It will be stored, dispensed and administered in accordance with standard NHS procedures and the SmPC (40). Midazolam is a licensed benzodiazepine used routinely to provide sedation and amnesia during medical procedures. It will be stored, dispensed and administered in accordance with standard NHS procedures and the SmPC (41). Lignocaine is a licensed local anaesthetic used routinely during medical procedures. It will be stored, dispensed and administered in accordance with standard NHS procedures and the SmPC (42). Other licensed drugs may be used during bronchoscopy at the discretion of the respiratory consultant performing the bronchoscopy and/or the investigators.

## 10. ASSESSMENT OF SAFETY

Safety will be assessed by the frequency, incidence and nature of AEs and SAEs arising during the study.

### 10.1 Definitions

#### 10.1.1 Adverse Event (AE)

An AE is any untoward medical occurrence in a volunteer, which may occur during or after administration of the BCG and does not necessarily have a causal relationship with the intervention. An AE can therefore be any unfavourable and unintended sign (including any clinically significant abnormal laboratory finding or change from baseline), symptom or disease temporally associated with the study intervention, whether or not considered related to the study intervention.

#### 10.1.2 Adverse Reaction (AR)

An AR is any untoward or unintended response to the challenge agent (BCG). This means that a causal relationship between the agent and an AE is at least a reasonable possibility, i.e., the relationship cannot be ruled out. All cases judged by the reporting medical investigator as having a reasonable suspected causal relationship to the agent (i.e. possibly, probably or definitely related to it) will qualify as AR.

#### 10.1.3 Unexpected Adverse Reaction

An adverse reaction, the nature or severity of which is not consistent with the applicable product information (e.g. SmPC).

#### 10.1.4 Serious Adverse Event (SAE)

An SAE is an AE that results in any of the following outcomes, whether or not considered related to the study intervention.

- Death
- Life-threatening event (i.e. the volunteer was, in the view of the investigator, at immediate risk of death from the event that occurred). This does not include an AE that, if it occurred in a more severe form, might have caused death.
- Persistent or significant disability or incapacity (i.e. substantial disruption of one's ability to carry out normal life functions).
- Hospitalisation, regardless of length of stay, even if it is a precautionary measure for continued observation. Hospitalisation (including inpatient or outpatient hospitalisation for an elective procedure) for a pre-existing condition that has not worsened unexpectedly does not constitute a serious AE.
- An important medical event (that may not cause death, be life threatening, or require hospitalisation) that may, based upon appropriate medical judgment, jeopardise the volunteer and/or require medical or surgical intervention to prevent one of the outcomes listed above. Examples of such medical events include allergic reaction requiring intensive treatment in an emergency room or clinic, blood dyscrasias, or convulsions that do not result in inpatient hospitalisation.
- Congenital anomaly or birth defect.

#### 10.1.5 Serious Adverse Reaction (SAR)

An AE (expected or unexpected) that is both serious and, in the opinion of the reporting investigator or sponsors, believed to be possibly, probably or definitely due to the challenge agent or any other study treatments, based on the information provided.

#### 10.1.6 Suspected Unexpected Serious Adverse Reaction (SUSAR)

A serious adverse reaction, the nature and severity of which is not consistent with the information about the medicinal product in question set out in the SmPC.

#### 10.2 Expectedness

No BCG related SAEs are expected in this study. All SARs will therefore be reported as SUSARs.

#### 10.3 Causality

For every AE, an assessment of the relationship of the event to the administration of BCG will be undertaken by the CI or delegated clinician. An interpretation of the causal relationship of the intervention to the AE in question will be made, based on the type of event; the relationship of the event to the time of BCG challenge; and the known biology of BCG (Table 5). Alternative causes of the AE, such as the natural history of pre-existing medical conditions, concomitant therapy, other risk factors and the temporal relationship of the event to BCG administration will be considered and investigated. Causality assessment will take place during planned safety reviews, interim analyses (e.g. if a holding or stopping rule is activated) and at the final safety analysis, except for SAEs, which should be assigned by the reporting investigator.

0	No Relationship	No temporal relationship to study product and Alternate aetiology (clinical state, environmental or other interventions); and Does not follow known pattern of response to study product
1	Unlikely	Unlikely temporal relationship to study product and Alternate aetiology likely (clinical state, environmental or other interventions) and does not follow known typical or plausible pattern of response to study product.
2	Possible	Reasonable temporal relationship to study product; or Event not readily produced by clinical state, environmental or other interventions; or Similar pattern of response to that seen with other challenge agents
3	Probable	Reasonable temporal relationship to study product; and Event not readily produced by clinical state, environment, or other interventions or Known pattern of response seen with other challenge agents
4	Definite	Reasonable temporal relationship to study product; and Event not readily produced by clinical state, environment, or other interventions; and Known pattern of response seen with BCG

**Table 5.** Guidelines for assessing the relationship of challenge administration to an AE.

#### 10.4 Reporting Procedures for All Adverse Events (see local SOP for AE reporting)

All AEs occurring in the 14 days following challenge and the 14 days following bronchoscopy observed by the investigator or reported by the volunteer, whether or not attributed to BCG, will be recorded on the diary card. Data from the diary cards will be extracted following the last volunteer last visit (LVLV) or at any time prior to this in order to perform an interim safety analysis. Outside the diary periods, respiratory and systemic AEs (listed in 6) will be specifically solicited at each visit, and graded by severity (as detailed in section 9.5). All AEs starting after the diary period(s), or persisting after this period, will be recorded in the AE line listing of the CRF.

Recording and reporting of all AEs will take place as detailed in SOP VC027 Adverse Event Data Collection and Analysis. All AEs that result in a volunteer's withdrawal from the study will be followed up until a satisfactory resolution occurs, or until a non-study related causality is assigned (if the volunteer consents to this). SAE will be collected throughout the entire study period.

Adverse event	
Respiratory	Cough
	Sore throat
	Tickly throat
	Wheeze
	Shortness of breath
	Coughing up phlegm
	Coughing up blood
	Chest tightness
	Chest pain
Systemic	Documented fever (oral temperature > 37.5° C)
	Myalgia
	Arthralgia
	Feverishness
	Headache
	Fatigue
	Nausea
	Malaise

**Table 6. Routinely solicited adverse events**

## 10.5 Assessment of severity

The severity of clinical and laboratory adverse events will be assessed according to the scales in table 7 and 8.

	Grade 1 (mild)	Grade 2 (moderate)	Grade 3 (severe)
Fever (oral)	37.6°C - 38.0°C	38.1°C – 39.0°C	>39.0°C
Tachycardia (bpm)*	101 - 115	116 – 130	>130
Bradycardia (bpm)**	50 – 54	40 – 49	<40
Systolic hypertension (mmHg)	141 - 159	160 – 179	≥180
Diastolic hypertension (mmHg)	91 – 99	100 – 109	≥110
Systolic hypotension (mmHg)***	85 – 89	80 – 84	<80

**Table 7. Severity grading criteria for physical observations.** \*Taken after ≥10 minutes at rest \*\*When resting heart rate is between 60 – 100 beats per minute. Use clinical judgement when characterising bradycardia among some healthy participant populations, for example, conditioned athletes. \*\*\*Only if symptomatic (e.g. dizzy/ light-headed)

GRADE 0	None
GRADE 1	Mild: Transient or mild discomfort (< 48 hours); no medical intervention/therapy required
GRADE 2	Moderate: Mild to moderate limitation in activity – some assistance may be needed; no or minimal medical intervention/therapy required
GRADE 3	Severe: Marked limitation in activity, some assistance usually required; medical intervention/therapy required, hospitalisation possible

**Table 8. Severity grading criteria for local and systemic AEs.**

## 10.6 Reporting Procedures for Serious AEs

All SAEs will be reported on the SAE forms to members of the study team immediately, once the Investigators become aware of their occurrence. Copies of all reports will be forwarded for review to the Chief Investigator (as the Sponsor's representative) within 24 hours of the Investigator being aware of the suspected SAE. The safety monitoring committee (SMC) chair will be notified of SAEs that are deemed possibly, probably or definitely related to study interventions; the SMC will be notified immediately (within 24 hours) of the Investigators' being aware of their occurrence. The funder will be informed of all SAE notifications reported to the SMC. SAEs will not normally be reported immediately to the ethical committee(s) unless there is a clinically important increase in occurrence rate, an unexpected outcome, or a new event that is likely to affect safety of study volunteers, at the discretion of the Chief Investigator and/or SMC.

A serious adverse event (SAE) occurring to a participant should be reported to the REC that gave a favourable opinion of the study where in the opinion of the Chief Investigator the event was 'related' (resulted from administration of any of the research procedures) and 'unexpected' in relation to those procedures. Reports of related and unexpected SAEs should be submitted within 15 working days of the Chief Investigator becoming aware of the event.

## **10.7 Procedures to be followed in the event of abnormal findings**

Eligibility for enrolment in the study in terms of laboratory findings will be assessed as detailed in SOP VC027. Abnormal clinical findings from medical history, examination or blood tests will be assessed as to their clinical significance throughout the study. Laboratory AEs will be assessed using the site-specific tables in SOP VC027. If a test is deemed clinically significant, it may be repeated, to ensure it is not a single occurrence. If a test remains clinically significant, the volunteer will be informed and appropriate medical care arranged as appropriate and with the permission of the volunteer. Decisions to exclude the volunteer from enrolling in the study or to withdraw a volunteer from the study will be at the discretion of the Investigator.

## **10.8 Interim Safety Reviews**

The safety profile of aerosol inhaled BCG will be assessed on an on-going basis by the investigators with communication to the SMC as necessary. The CI and relevant investigators (as per the study delegation log) will also review safety issues and SAEs as they arise.

The SMC will be consulted to provide a review of safety data and adverse events at least 7 days following completed enrolment of each group and prior to proceeding to dose escalation. All reports to the SMC will be shared with the funder.

## **10.9 Safety Monitor Committee**

An independent Safety Monitoring Committee (SMC) will be appointed to provide real-time safety oversight. The SMC will be notified within 24 hours of the investigators' being aware of the occurrence of SAEs. The SMC has the power to place the study on hold if deemed necessary following a study intervention-related SAE. The SMC will be chaired by [name] with [name] and [name] as committee members. All correspondence between the investigators and SMC will be conveyed by the investigator to the study sponsor or their delegate. The Chair of the SMC will be contacted for advice and independent review by the investigator or study sponsor in the following situations:

- Following any SAE deemed to be possibly, probably, or definitely related to BCG.
- Prior to dose escalation occurring
- Any other situation where the investigator or study sponsor feels independent advice or review is important

## **10.10 Safety Group Holding Rules**

Safety holding rules have been developed to take into account the fact that this is a dose escalation study of aerosolised BCG in BCG historically-vaccinated volunteers. Solicited AEs are those listed as foreseeable AEs in section 10.4 of the protocol. Unsolicited adverse events are adverse events other than these foreseeable AEs.

#### 10.10.1 Group holding rules

The following would act as a trigger to place the study on hold and the SMC would need to be consulted prior to recommencement:

- Solicited local (respiratory) adverse events: If more than one dose of the challenge agent is followed by the same grade 3 solicited local AE beginning within 2 days after challenge (day of challenge and one subsequent day) and persisting at Grade 3 for >48 hours.
- Solicited systemic adverse events: If more than one dose of the challenge agent is followed by the same grade 3 solicited systemic AE beginning within 2 days after challenge (day of challenge and one subsequent day) and persisting at grade 3 for >48 hours.
- Unsolicited adverse events: If more than one volunteer develops a grade 3 unsolicited AE (that is considered possibly, probably or definitely related to challenge) and persists at grade 3 for >48 hours.
- Laboratory adverse event: If more than one volunteer develops the same grade 3 laboratory AE considered possibly, probably or definitely related that persists at grade 3 for >72 hours
- Any serious adverse event considered possibly, probably or definitely related to the challenge agent occurs
- Death considered possibly, probably or definitely related to challenge occurs
- A life-threatening reaction considered possibly, probably or definitely related to challenge occurs

Communication of any study pauses will be shared with the funder.

Previously, we had planned to wait 14 days after challenge prior to safety review and further challenge or dose escalation, based on timing of AEs collected in TB041 (NCT02709278). Mild local (respiratory) solicited AEs were seen to continue for at least 2 weeks in several volunteers (volunteers underwent bronchoscopy at 2 weeks, so local AEs seen after this would be expected due to this procedure). A possible small increase in systemic solicited AEs was seen at around day 13. Several unsolicited AEs of grade 1 or 2 “chest tightness” were seen around the day 8-12 mark and the 14 day review period was planned in TB044 in case there was a clustering of chest symptoms around the Day 10 mark.

Chest tightness was added as a solicited symptoms in TB043. As groups 1 and 2 in TB043 underwent a bronchoscopy prior to day 14, this significantly confounded the adverse event profile in the first two weeks. Now we have further data from groups 3-5 in TB043, who do not undergo bronchoscopy until after the initial 14 days solicited symptoms diary is complete. This data has shown no evidence of late clustering of chest symptoms or other adverse events. In all of these TB043 volunteers who have received  $1 \times 10^7$  BCG (n=20), there has been no chest tightness reported after Day 7. There have been no reported respiratory AEs above a Grade 1 after Day 6 (Figure 5). There has been no evidence of a clustering of respiratory symptoms around the Day 10 timepoint, and therefore we plan to shorten our safety review duration to 7 days, in keeping with more normal practice in dose escalation or first in human studies.

[figure not shown]

Figure 5. TB043. Solicited AE within 2 weeks of aerosol BCG ( $1 \times 10^7$ ) or saline placebo

If a holding rule has been met and, following an internal safety review by the SMC it is deemed appropriate to restart dosing, a request to restart dosing with pertinent data will be submitted to the REC. The internal safety review will consider:

- The relationship of the AE or SAE to the challenge agent.
- The relationship of the AE or SAE to the challenge dose, or other possible causes of the event.
- If appropriate an amendment will be submitted, for example with additional screening or laboratory testing for other volunteers to identify those who may develop similar symptoms and alterations to the current Participant Information Sheet (PIS) if required.

The local ethics committee will be notified if a holding rule is activated or released.

All enrolled volunteers will be followed for safety until resolution or stabilisation (if determined to be chronic sequelae) of their AEs, providing they consent to this.

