## 6. STUDY DESIGN

This is a phase I dose-escalation clinical challenge study in historically BCG-vaccinated healthy adult volunteers in which BCG will be administered via the aerosol inhaled route.

There will be four study groups with three volunteers in each group (Table 2). Volunteers will be sequentially enrolled into each group in turn based on their availability. The first volunteer in each group will be challenged at least 1 hour apart from any subsequent volunteers. There will be a review of safety data at least 7 days after challenge of all volunteers within each dose group. This safety review will be performed by the Safety Monitoring Committee (SMC). Dose escalation into the next group will only occur if there are no safety concerns. Safety review will include assessment of symptom diary card, safety bloods and lung function results.

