#### **8.6 Diary Card**

Following the BCG challenge, volunteers will be asked to complete a diary card, which may be in paper or electronic format. Volunteers will be asked to record any specific solicited and unsolicited AEs daily, for 28 days. Diary cards will be reviewed with volunteers at the post-challenge follow up visits.

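### More than one volunteer could have the same related, non-serious grade 3 solicited AE starting on Day 2 or later and meet no pre-defined holding rule, because both solicited rules count only Day 0 and Day 1 onsets

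*Combined protocol and SAP*

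**What the plan says.** Section 10.10.1 lists what places the study on hold until the SMC has been consulted. The solicited respiratory rule needs more than one dose to be followed by "the same grade 3 solicited local AE beginning within 2 days after challenge (day of challenge and one subsequent day", with the event staying at grade 3 for over 48 hours. The systemic rule is worded the same way. With challenge as Day 0, both windows are Day 0 and Day 1. Neither rule asks whether the event is related. The unsolicited and laboratory rules have no onset limit but count only related events. A single related SAE, death or life-threatening reaction is enough at any time.

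Section 10.10 separates the two classes by type: "Unsolicited adverse events are adverse events other than these foreseeable AEs". The foreseeable AEs are those listed in section 10.4 (Table 6), and section 10.4 still treats them as solicited at visits outside the diary periods.

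The surrounding oversight is as follows. The SMC reviews safety data "at least 7 days following completed enrolment of each group and prior to proceeding to dose escalation" (section 10.8). Section 6 says that this review includes the diary card and that "Dose escalation into the next group will only occur if there are no safety concerns". Other communication with the SMC is left to need. On non-serious AEs, section 10.3 says: "Causality assessment will take place during planned safety reviews, interim analyses" and the final analysis; only SAEs have causality assigned by the reporting investigator. Section 8.6 adds: "Diary cards will be reviewed with volunteers at the post-challenge follow up visits".

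Section 10.10.1 also explains the review interval. In TB041, several unsolicited reports of grade 1 or 2 chest tightness "were seen around the day 8-12 mark and the 14 day review period was planned in TB044". TB043 later showed "no evidence of a clustering of respiratory symptoms around the Day 10 timepoint, and therefore we plan to shorten our safety review duration"; the minimum is now one week.

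**The concern.** The onset limit and the definition by type interact. A listed symptom that starts on Day 2 or later is too late for the solicited rules and of the wrong type for the unsolicited rule. Section 10.10.1 does not explain why a late listed symptom should count for less than a late unlisted one.

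Chest tightness shows the effect. In TB041 it was recorded as unsolicited; it has been solicited since TB043 and is solicited here. The symptom that once led the sponsor to plan a 14-day review has thus moved from a class with no onset limit to one limited to two days.

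At stake is whether a repeated, related, severe late reaction leads to a pause automatically or only if someone decides to raise it. The sponsor describes this as its first trial of aerosolised BCG in previously vaccinated volunteers (section 4.6).

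**Working it through.** **The plan's own figure.** Four groups of three give 4 × 3 = 12, which reproduces. The plan states no operating characteristic for the holding rules.

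**The rules side by side (section 10.10.1).**

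| Rule | Events needed | Time at grade 3 | Onset limit | Must be related? |
|---|---|---|---|---|
| Solicited respiratory | same AE after more than one dose | >48 h | Day 0-1 | no |
| Solicited systemic | same AE after more than one dose | >48 h | Day 0-1 | no |
| Unsolicited | more than one volunteer | >48 h | none | yes |
| Laboratory | same AE, more than one volunteer | >72 h | none | yes |
| SAE, death, life-threatening | one | not applicable | none | yes |

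**Test case.** Two volunteers have related, non-serious grade 3 chest tightness lasting three days.
- Onset on Day 1: the respiratory rule is met.
- Onset on Day 10: the respiratory rule fails on onset, the unsolicited rule fails on type, and the systemic, laboratory and last-row rules do not apply. No rule is met.
- Same facts on Day 10 with an unlisted symptom such as palpitations: the unsolicited rule is met.
- Only one volunteer affected, on Day 1 or Day 10: no rule is met either way. The window therefore matters only for two or more matching events.

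**Extent.** Solicited types: 9 respiratory + 8 systemic = 17. Onset days from Day 0 to Day 14: 15. The solicited rules cover 2 and leave 13. Of these, Days 2-7 (6 days) come before or at the earliest permitted SMC review, and Days 8-14 (7 days) may come after it. The visit after Day 7 is the Day 14 visit, with a window of -5 to +21 days (Table 4), so about Day 9 to Day 35.

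**Illustration.** The documents give neither the risk *p* that a volunteer has the same persistent grade 3 solicited AE nor the share *f* of such events starting on Day 0-1. Both are assumed here, with *p* constant across doses. The chance that the present solicited rule fires over the trial is P(X ≥ 2), X ~ Binomial(12, *p* × *f*):

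| *p* | *f* = 1 | *f* = 0.5 | *f* = 0.25 | *f* = 0 |
|---|---|---|---|---|
| 0.05 | 0.118 | 0.035 | 0.009 | 0 |
| 0.10 | 0.341 | 0.118 | 0.035 | 0 |
| 0.20 | 0.725 | 0.341 | 0.118 | 0 |

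If every onset is late, the solicited rules never fire, whatever *p* is. An added late-onset rule would then restore the *f* = 1 column, provided that all events are judged related and not due to bronchoscopy. Within one group of three, the *f* = 1 figures are 0.007, 0.028 and 0.104.

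**How likely late events are.** Section 10.10.1 reports, for 20 TB043 volunteers given 1×10^7 cfu, no chest tightness after Day 7 and no respiratory AE above grade 1 after Day 6. For 0/20, the exact upper 95% limit is 1 - 0.05^(1/20) = 13.9% one-sided, or 1 - 0.025^(1/20) = 16.8% two-sided. Late grade 3 respiratory AEs are a subset of these, so the limit applies to them too, but in BCG-naive volunteers (Lay Summary).

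**Workload of notification.** The expected number of notifications is 12 × (assumed risk of a related late grade 3 solicited AE): 0% gives 0, 5% gives 0.6, 10% gives 1.2 and 16.8% gives 2.0. The documents give no such rate for vaccinated volunteers, nor one for late systemic AEs.

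**The case against.** The strongest reply is that the asymmetry is deliberate. The solicited rules need no relatedness judgement, so a short window stands in for causality; the unsolicited and laboratory rules drop the window but require relatedness. This is a sound reason to keep the Day 0-1 rules as they are. It does not explain why a late solicited AE that *is* judged related should count under neither scheme.

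Second, the gap is narrow. Section 10.1.4 makes admission for observation an SAE and includes important medical events. Table 8 describes grade 3 as needing medical intervention. Late wheeze or haemoptysis might well qualify as serious, and one related SAE holds the study. Section 10.9 lets the SMC chair be consulted whenever the investigator or sponsor thinks it important, section 10.10.2 allows a hold for any event, and volunteers have a 24-hour number (section 8.7.3.1). All of this stands and limits the size of the point. After a group's review, however, these routes depend on judgement, apart from the related-SAE rule and the next escalation review.

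Third, a reader might infer that the 7-day interval is unsafe. The documents do not support that: TB043 showed no late clustering of chest symptoms or other AEs, and a study instilling 10^4 cfu bronchoscopically in BCG-vaccinated people saw no hypersensitivity reactions (section 4.4).

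Fourth, a reader might want grade 2 late events referred as well, since the TB041 chest tightness was grade 1 or 2. That would act as a dosing gate on a low bar: section 10.3 allows a rating of possible on a reasonable temporal relationship alone. It would also put one brief grade 2 event on Day 10 ahead of a persistent grade 3 event from Day 0. It is not recommended.

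**Conclusion.** The concern holds as a gap in the pre-defined triggers. More than one volunteer with the same related, non-serious grade 3 solicited AE, starting on Day 2 or later and lasting over 48 hours, meets no holding rule, although equivalent unsolicited AEs would. It affects 17 AE types and 13 of the 15 onset days to Day 14. In practice it matters most for onsets after a group's SMC review, which can include all of Days 8-14 when the minimum interval is used.

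Two wider readings fail. Late events do not escape oversight: the escalation reviews, the related-SAE rule and the discretionary hold remain, and groups 2 to 4 each follow a mandatory SMC review. Nor is every late grade 3 event treated worse than an early one, since a single non-serious event triggers nothing on either side of the window.

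This is a cheap improvement. The documents report no late grade 3 event, and the probabilities above rest on assumed values of *p* and *f*. The reading of the rules rests on the protocol text alone; the AE reporting SOP (VC027) and the SMC report format are not shown and might add detail.

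**What to change.** Leave the Day 0-1 solicited rules and the 7-day interval unchanged. Add to sections 10.8 and 10.10.1, with a matching exception in section 10.3:

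1. A grade 3 solicited AE that begins later than the day after challenge, is rated possible, probable or definite in relation to BCG, and is not explained by bronchoscopy, is notified to the SMC chair when reported. The investigator assigns causality at that time, as for SAEs.
2. If more than one volunteer has such an AE and it stays at grade 3 for more than 48 hours, the study is placed on hold on the same terms as for unsolicited AEs.
3. As a supporting clarification, each SMC escalation report lists AEs by onset day for all groups dosed so far.

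The bronchoscopy condition is needed because Appendix A records cough in 86% of volunteers after the procedure (12 × 0.86 = 10.3, about 10 of 12; grades not given).

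The cost is a few sentences and onset day in the SMC listing. No new data are needed: the diary records timing and severity (section 8.7.3.1) and reaches Day 14 on either stated length (28 days in section 8.6; 14 days in sections 10.4 and 12.1). The sample size is unchanged. The downside is a probably rare extra SMC contact or short delay, and an earlier causality judgement for these events.
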